3.3. Study size

All analyses (except the estimation of the prevalence of AF) will be conducted in patients newly diagnosed with FA. In 2018, a study conducted by Santé Publique France, showed that 225,747 AF patients were OAC new users (6). If the number of new patients remains constant during the study period of 5 years from 2016 to 2020, we expect that approximately 1 million patients will be exposed to OAC in the SIFNOS study.

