9.2.1.1 Inclusion period

Within the extraction period, the inclusion period is from January 1st, 2016 to December 31st, 2019 and to December 31st, 2020 for sensitivity analyses.

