9.5 Study Size

All analyses (except the estimation of the prevalence of NVAF) will be conducted in patients newly diagnosed with FA. In 2018, a study conducted by Santé Publique France, showed that 225,747 NVAF patients were OAC new users (6). If the number of new patients remains constant during the study period of 5 years from 2016 to 2020, we expect that approximately 1.3 million patients will be exposed to OAC in the SIFNOS study.

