Censor is defined as patient's last health record, or date of end of follow-up. Hazard ratios and associated 95% CI will be reported. Models will be considered valid if they meet the proportional hazards assumption as assessed by examination of Schoenfeld residuals and log-log plots. In case of the proportionality assumption is violated, the nonparametric additive hazard model (Aalen-model) with OAC exposure considered as time-dependent variable will be applied.

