3.3. Comparison of the incidence of stroke, major bleeding, death

Table A10. Risk of stroke, major bleeding or death in AF incident patients

	Event		Crude risk ¹		Adjusted risk ^{2,*}	
	n	%	HR	[95%CI]	HR	[95%CI]
Risk of stroke						
Exposure to DOACs	xx	(x.x)	x.xx	[x.xx-x.xx]	x.xx	[x.xx-x.xx]
Exposure to Apixaban	xx	(x.x)	x.xx	[x.xx-x.xx]	x.xx	[x.xx-x.xx]
Exposure to Dabigatran	xx	(x.x)	x.xx	[x.xx-x.xx]	x.xx	[x.xx-x.xx]
Exposure to Rivaroxaban	xx	(x.x)	x.xx	[x.xx-x.xx]	x.xx	[x.xx-x.xx]
Unexposed to OAC**	xx	(x.x)	x.xx	[x.xx-x.xx]	x.xx	[x.xx-x.xx]
Exposure to VKA	xx	(x.x)	ref		ref	
Risk of major bleeding						
Exposure to DOACs	xx	(x.x)	x.xx	[x.xx-x.xx]	x.xx	[x.xx-x.xx]
Exposure to Apixaban	xx	(x.x)	x.xx	[x.xx-x.xx]	x.xx	[x.xx-x.xx]
Exposure to Dabigatran	xx	(x.x)	x.xx	[x.xx-x.xx]	x.xx	[x.xx-x.xx]
Exposure to Rivaroxaban	xx	(x.x)	x.xx	[x.xx-x.xx]	x.xx	[x.xx-x.xx]
Unexposed to OAC**	xx	(x.x)	x.xx	[x.xx-x.xx]	x.xx	[x.xx-x.xx]
Exposure to VKA	xx	(x.x)	ref		ref	
Risk of death						
Exposure to DOACs	xx	(x.x)	x.xx	[x.xx-x.xx]	x.xx	[x.xx-x.xx]
Exposure to Apixaban	xx	(x.x)	x.xx	[x.xx-x.xx]	x.xx	[x.xx-x.xx]
Exposure to Dabigatran	xx	(x.x)	x.xx	[x.xx-x.xx]	x.xx	[x.xx-x.xx]
Exposure to Rivaroxaban	xx	(x.x)	x.xx	[x.xx-x.xx]	x.xx	[x.xx-x.xx]
Unexposed to OAC**	xx	(x.x)	x.xx	[x.xx-x.xx]	x.xx	[x.xx-x.xx]
Exposure to VKA	xx	(x.x)	ref		ref	

AF : Non Valvular Atrial Fibrillation; HR: hazard ratio; 95%CI: 95% confidence interval

Note: For considering DOAC treatment in models, two regressions models will be performed for this table: one model with "Exposure to DOACs" as independent variable; second model with exposure for each molecule within the class of DOAC (Apixaban, Dabigatran, Rivaroxaban).¹From a time-dependant exposure to OAC Cox proportional hazards model

²From a time-dependant exposure to OAC and time-fixed covariates Cox proportional hazards model;

*Adjusted on the following covariates at index date: age (<80, 80-90, >90 years old), sex, having malnutrition, risk of falls, morbid obesity, history of stroke, history of major bleeding, at least one visit to a nursing home, history of dementia, each concomitant treatments

**Unexposed to OAC correspond to the period where the patients are not exposed to OAC.

Same table will be presented for sensitivity analyses:

- with integration of 2020 data

- with 30 days and 90 days of maximal number of days allowed for being refilled

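### The proportional-hazards check for objective 3 has no criterion, and its Aalen fallback has no result table, so the effect scale can be settled after the data are seen

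*SAP*

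**What the plan says.** SAP 9.7.4.2 fits a separate Cox model for each of stroke, major bleeding and death. OAC exposure is time-dependent, VKA is the reference, and the covariates are fixed at index. The effect measure is stated without condition: "Hazard ratios and associated 95% CI will be reported". Two sentences then govern model checking. The first is "Models will be considered valid if they meet the proportional hazards assumption as assessed by examination of Schoenfeld residuals and log-log plots". The second is "In case of the proportionality assumption is violated, the nonparametric additive hazard model (Aalen-model) with OAC exposure considered as time-dependent variable will be applied".

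The section gives no test, significance level or tolerable size of departure. It does not say whether the check covers the exposure terms only or every covariate, or whether the Cox HRs are still shown after a violation.

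Table A10 ("Risk of stroke, major bleeding or death in AF incident patients") and Table A11, its high-thromboembolic-risk counterpart, have columns for events, crude HR and adjusted HR, all footnoted to Cox models. Table XXI lists only the Cox model for objective 3. Protocol 3.7.2.2 plans Cox HRs with time-dependent exposure (IPTW if necessary), and has neither a validity condition nor an Aalen model.

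**The concern.** Making validity depend on the assumption turns a diagnostic into a switch between two estimands. A Cox model gives a ratio of hazards. An Aalen model gives cumulative additive coefficients, that is, rate differences accumulated over follow-up. Neither converts into the other, and the SAP names no Aalen summary measure, time point or table.

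Because the threshold is undefined, the analyst must decide after seeing the residuals whether the assumption is violated. Each outcome is modelled separately, so stroke could be reported as an HR and death as a rate-difference curve. Table A10 is repeated with the 2020 data, with 30- and 90-day refill gaps, and with all incident patients. If the switch is applied run by run, a main result and its own sensitivity analyses may not be comparable. Objective 3 is secondary, but it is the study's only covariate-adjusted comparison of the clinical outcomes.

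**Working it through.** **1. The texts side by side.** After a violation, one sentence promises HRs, another implies that the model producing them is not valid, and a third brings in a model that produces none. The shells accept HRs only. The SAP does not say which sentence prevails.

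**2. The diagnostics.** A log-log plot compares survival curves of fixed groups. Under SAP Table VII, patients move between OAC and unexposed sequences, so no fixed groups exist for the exposure of interest. Scaled Schoenfeld residuals are computed at event times from the current risk set and do accommodate a time-dependent exposure. One of the two named tools is therefore usable for exposure.

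**3. Study size.** The only size input is 225,747 OAC new users per year. Over five years, 225,747 × 5 = 1,128,735. The SAP says "approximately 1.3 million patients will be exposed to OAC in the SIFNOS study" and the protocol says "approximately 1 million patients will be exposed to OAC in the SIFNOS study"; the product is 13.2% below the former and 12.9% above the latter, so neither figure is reproduced. That mismatch is a separate matter. In the main analysis "the inclusion period is from January 1st, 2016 to December 31st, 2019 and to December 31st, 2020 for sensitivity analyses", so I use four years: 225,747 × 4 = 902,988. This counts OAC new users only; never-treated patients would add events.

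**4. Event counts (assumed; the documents give none).** With 1–5 events per 100 person-years and mean follow-up of 1.5–2 years:
- low: 902,988 × 1.5 × 0.01 = 13,545, taken as 13,500
- middle: 902,988 × 2 × 0.02 = 36,120, taken as 36,000
- high: 902,988 × 2 × 0.05 = 90,299, taken as 90,000

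**5. What a formal 5% test would do, if one were used.** Take two periods with half the events in each. Let D be the number of events, p the share in one group, and r the ratio of the late to the early HR. Then z = |ln r| × √(D·p·(1−p)/4), and the chance of a flag is Φ(z − 1.96) + Φ(−z − 1.96).

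Example: D = 13,500, p = 0.10, r = 1.10 gives z = 0.0953 × √303.75 = 1.66, and a chance of 0.383.

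| Events | Group share | 5% drift | 10% drift | 20% drift |
|---|---|---|---|---|
| 13,500 | 5% | 0.095 | 0.226 | 0.636 |
| 13,500 | 10% | 0.136 | 0.383 | 0.888 |
| 13,500 | 20% | 0.205 | 0.601 | 0.989 |
| 36,000 | 5% | 0.172 | 0.504 | 0.965 |
| 36,000 | 10% | 0.284 | 0.774 | 0.999 |
| 36,000 | 20% | 0.457 | 0.951 | 1.000 |
| 90,000 | 5% | 0.358 | 0.876 | 1.000 |
| 90,000 | 10% | 0.593 | 0.990 | 1.000 |
| 90,000 | 20% | 0.833 | 1.000 | 1.000 |

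For a group with 10% of events, the drift detected with 80% power is a ratio of 1.17, 1.10 and 1.06 at the three event counts.

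**6. Cross-check.** A simulated rank-time Schoenfeld test of one binary covariate, with the HR changing after year 1 and about 34,000 events, flagged a 10% change in about 0.53 of runs (10% share) and 0.70 (20% share). A 20% change was flagged in 0.98 and 1.00. These rest on 40 runs each. For the 10% change they lie below the closed form at 36,000 events (0.774 and 0.951), which assumes equal periods aligned with the change. The direction is the same.

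**The case against.** The strongest reply is that the SAP asks for examination of residuals and plots, not a significance test. Looking at a smoothed residual curve does not reject merely because the database is large. The 5% level in SAP 9.7.4.5 belongs to the cost comparison. This stands, and it rules out one inference a reader might draw: that the check will almost always fail. Even with a 5% test, the chance of a flag runs from about 0.10 to 1.00 over the assumed counts, shares and drifts.

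A reader might also count terms. Table XV gives 28 (11 items plus 17 concomitant treatments), exposure makes 29, and the histories of stroke, bleeding and dementia in 9.7.4.2 make 32. That gives 1 − 0.95^29 = 77% to 1 − 0.95^32 = 81% for at least one false flag. But this needs a 5% test on every term, and independence. The SAP plans no such tests, and age, CHA2DS2-VASc, HAS-BLED and the age-adjusted Charlson index share components. The Table A10 footnote supports only 27 terms (9 covariates, 17 treatments, exposure).

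A second tempting reading is that the SAP drops the HRs. It does not say so: it promises them without condition and says the Aalen model will be applied, not that it replaces them. A third is that exposure goes unchecked; the Schoenfeld residuals answer that.

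What remains is that judging by eye, with no stated threshold, leaves the choice of scale open until the data are seen. Missing columns could be added to the shells, but the missing estimand would still have to be chosen.

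**Conclusion.** The concern holds in a limited form. The text alone shows that a violation is undefined, that the fallback is on a different scale with no summary measure or table, that the three outcomes and the sensitivity runs can diverge in scale, and that log-log plots do not suit the exposure. None of this rests on an assumed figure.

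The size is conditional. If a formal 5% test were adopted, a 10% drift in a group with 10–20% of events would be flagged 38–60% of the time at 13,500 events and 99–100% at 90,000. This rests on assumed event rates, follow-up, group shares and an equal split of events between periods. Whether a 10% drift matters clinically is a judgement the SAP should make in advance.

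The documents support neither near-certain failure of the check nor a definite loss of the HRs. The primary objective uses person-year rates and is unaffected. This should be changed before analysis, and is cheap to change.

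**What to change.** Rewrite the model-checking paragraph of SAP 9.7.4.2 as follows.

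- Remove the validity condition. Report the Cox HR with 95% CI for stroke, bleeding and death, in the main and every sensitivity run, as the planned time-averaged estimate.
- Assess exposure with smoothed scaled Schoenfeld residuals and drop the log-log plots. State in advance what change in the smoothed HR counts as a departure.
- Where exposure departs, add HRs for periods since index as extra rows in Tables A10 and A11. Fix the cut-points before data access (0–3, 3–12 and over 12 months is one example).
- Where an adjustment covariate departs, stratify the baseline hazard on it. The exposure effect stays on the HR scale.
- Keep the Aalen model, if wanted, as an optional supplement that does not replace the HRs.

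The cost is SAP wording, an exposure-by-period interaction where needed and some table rows. The downside is that the average HR needs an interpretive note when the period HRs differ. A borderline call on departure then costs extra rows and no longer changes the scale of the result.

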9.7.4.3 Estimation of the annual standardized incidence rate and prevalence

The analysis of annual standardized incidence rate and prevalence of diagnosed AF patients in France in 2016, 2017, 2018 and 2019 will be descriptive in nature and will be performed for each calendar year, from 2016 to 2020.

Prevalent and incident patients with an AF diagnosis will be the patients with a diagnosed NVAF during the historical period and the patients newly diagnosed AF during the inclusion period. The estimations of the prevalence and incidence of AF will be based on the count of patients living in France as denominator (based on socio-demographic data published by the National Institute for Statistics and Economic Studies (INSEE) and will be expressed per 100,000 inhabitants.

The analysis will include the following measures for summarizing the information on the prevalence and incidence of diagnosed AF patients, for each calendar year between 2016 and 2019 in France:

- Overall count of prevalent and incident of diagnosed AF patients in year Y, separately
- Overall crude prevalence and cumulative incidence of diagnosed AF patients in year Y, separately; computed as:

$$CP_Y = \frac{\text{count of prevalent diagnosed NVAF patients in year Y}}{\text{count of French adult residents from census data in year Y}} \times 100,000$$

- CP_Y represents the crude prevalence of diagnosed AF patients in the year Y
- Y represents the year of interest

$$CI_Y = \frac{\text{count of incident diagnosed NVAF patients in year Y}}{\text{count of patients at risk in year Y}} \times 100,000$$

- CI_Y represents the cumulative incidence of diagnosed NVAF patients in the year Y
- Y represents the year of interest
- *Count of patients at risk* represents French adult residents from census data in year Y minus count of prevalent diagnosed NVAF patients in year Y

- Overall age-standardized cumulative incidence of diagnosed AF patients in year Y computed as:

$$age - SCI_Y = \frac{\sum_i CI_{i,Y} \times N_{i,Y}}{\sum_i N_{i,Y}} \times 100,000$$

- $age - SCI_Y$ represents the age-standardized cumulative incidence of diagnosed AF patients in year Y
- i represents the age group (<65 years old / 65-74 / 75-79 / \geq 80 years)
- Y represents the year of interest
- $CI_{i,Y}$ represents the crude cumulative incidence of diagnosed AF patients in the age group i in the year Y
- $N_{i,Y}$ represents the counts of patients at risk (French adult residents from census data in year Y minus count of prevalent diagnosed AF patients in year Y) in the age group i in the year Y

The estimations of the annual standardized incidence and annual prevalence of AF will be also performed according to exposure status (exposed to OAC or unexposed), every year. A patient will be considered exposed to OAC in a given year if the patient presents at least one sequence treatment for an OAC in the corresponding year.

9.7.4.4 Description of the use of oral anticoagulants (OACs) in AF incident patients initiating treatment (AF patients exposed to OAC therapy)

The analysis of the OAC treatment patterns will be descriptive and exploratory in nature.

The date of first reimbursement of any drugs of interest (VKA, apixaban, rivaroxaban, and dabigatran) will be considered as the regimen initiation date and mark the beginning of the identification of the treatment sequence (cf. table VII).

The duration of a prescription will be of 30 days for any drugs of interest. The grace period considered for any drugs of interest considered will be 60 days (30 days and 90 days will be considered for sensitivity analyses).

A treatment sequence will continue until one of the following occurs:

- A regimen switch, defined as the reimbursement of another OAC. The end date of the first treatment sequence is the day before the date of first reimbursement of another OAC.
- Discontinuation of drugs in the treatment sequence: if a period between two consecutive claims is superior to the duration of the treatment of the last claim, plus a permissible gap of at least 60 days (30 and 90 days for sensitivity analyses) then the medication is considered as stopped within the treatment sequence. The date of discontinuation (end date of the treatment sequence) will be fixed at the date of the last claim, plus the treatment duration of this last claim.
- End of follow-up.

The treatment pattern analysis will be providing the following information:

- Number and percentage of patients receiving each of OAC treatment during the follow-up
- Number and percentage of patients who received 1, 2, 3, 4 and 5+ sequence treatment during the follow-up
- Number and percentage of patients who have switched from an OAC to another during the follow-up
- Number and percentage of patients who have concomitant treatments during the follow-up (cf. Table XIV. Derived variables for concomitant treatments).
- Number and percentage of patients who have a temporary or permanent discontinuation during the follow-up
- Number and percentage of the type of structure (hospital or private medical practice) and type of prescriber's specialty (generalist, city cardiologist or other) for each OAC and for each treatment exposure sequence (1/2/3/4/5+)
- Analyses of duration of treatment for each OAC (only median (Q1/Q3) and min/max will be presented).
- Time to next treatment (TTNT) changed for each OAC

Sunbursts (example in fig. A2) will be used to illustrate treatment pattern sequence.

Persistence rate at 6 and 12 months after initiation of each OAC and any OAC will be estimate with Kaplan-Meier curves (example in fig. A3). Persistence rate will be defined as no interruption of treatment sequences during follow-up (at 6 and 12 months) from the date of first OAC delivery. Patients will be considered non-persistent at the occurrence of the first treatment sequence end during follow-up.

- For persistence rate of overall OAC, switching from one DOAC therapy to VKA therapy will not be considered as a treatment discontinuation.
- For persistence rate of each OAC, switching from one OAC therapy to another OAC will not be considered as a treatment discontinuation.
- In the case of persistence rate for DOAC overall or VKA overall, switching from one DOAC therapy to VKA will be considered as a treatment discontinuation, and inversely.

Similarly, to sequence treatments, sensitivity analysis will be performed to test the impact of different gaps on the measurement of persistence rate using a 30- and 90-day gap (i.e. grace period).

9.7.4.5 Comparison of Healthcare Resource Utilization (HCRU) and associated costs between patients exposed to apixaban, rivaroxaban, dabigatran, VKA and patients unexposed to OACs

HCRU and associated costs including event-related costs (i.e. stroke related and/or bleed related), will be described overall and for each resource (ambulatory care, hospital care, rehabilitation care facilities and medications) at every calendar year of follow-up for AF incident patients exposed to apixaban, rivaroxaban, dabigatran, VKA and unexposed to OAC from index date to end of follow-up, including number and rate of patients using each resource by year of follow up in term of :

- Counts and percentages of patients with at least 1 reimbursement of specific OAC or no reimbursement for patients unexposed to OAC.
- Mean, SD, median, Q1, Q3, min and max of the rate of reimbursements per patient per month of follow-up in patients with at least 1 reimbursement of specific OAC or no reimbursement for patients unexposed to OAC.

All costs will be provided in Euros, annualized based on 2019 prices and presented per patients per month (PPPM) to consider differences in follow-up duration. Cost analysis will be performed from the health insurance perspective (reimbursed costs).

For the comparison of average of the overall PPPM costs (e.g. during all the follow-up) between AF incident patients exposed to apixaban, rivaroxaban, dabigatran vs NVAF patients exposed to VKA, significant differences between groups will be detected with an ANOVA for global equality of means. In case of the global test is significant, Tukey post-hoc test will be calculated to evaluate pair comparison. Normality will be tested before processing the analyses by the evaluation of the residuals (QQ plot and Shapiro-Wilk test) and homogeneity of variance with the Levene test and the plot of residuals versus fits. If normality not verified, Kruskal-Wallis test will be used. If homogeneity not verified, the Welch ANOVA will be used and Games-Howell for post-hoc test. The tests will be two-sided with a significance level of 5%.

9.7.4.6 Description of the therapeutic management before/after the first stroke occurring after initiation of OAC therapy

HCRU overall and for each resource (ambulatory care, hospital care, rehabilitation care facilities and medications) will be described at 6 and 12 months before and after the first stroke occurring after initiation of OAC therapy for patients exposed to apixaban, rivaroxaban, dabigatran and VKA in term of :

- Counts and percentages of patients with at least 1 reimbursement HCRU.

- Mean, SD, median, Q1, Q3, min and max of the rate of reimbursements per patient per month of follow-up in patients with at least 1 reimbursement of HCRU.

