Parameter	Description/Definition
Sociodemographic characteristics	Age, sex, complimentary universal health care (CMU-c), aid for complementary health care (ACS) for elderly patients, department of patient's residence
Medical history and comorbidities	Identified algorithmically with hospital diagnoses, active long-term disease, drugs and medical procedures: Coronary arterial diseases (CAD), Dementia (Alzheimer dementia/vascular dementia/other dementia), Ischemic or hemorrhagic stroke (intracranial bleeding) Congestive Heart failure, Peripheral arterial disease, Other vascular diseases; Sleep disorders; Active cancer (within 6 months in the historical period) Age adjusted Charlson Cormordity Index (ACCI) adapted to the SNDS data (20) ; Frail patient identified by Claims-Based Fragility Index (CFI) adapted to the SNDS data (21) ; Malnutrition ; Morbid Obesity; Anemia; COPD Diabetes Patients at risk of falls identified by an algorithm adapted to SNDS data (22) ; Patients poly-medicated Patient with at least one nursing home entry available
Drug exposure	AF patients exposed to VKA, apixaban, rivaroxaban, dabigatran AF patients unexposed to OAC
Associated treatments	Beta-blockers, antihypertensives, antiplatelet drugs, other anticoagulants, Non-steroidal anti-inflammatory drugs (NSAIDs), oral corticoids, proton pump inhibitors, Selective serotonin reuptake inhibitor antidepressants (SSRIs), systemic azole antifungals, medical procedure of cardioversion, CYP P450 inhibitors, protease inhibitors
Left atrial appendage (LAA) occlusion	Medical procedure of treatment of thromboembolic risk in AF in alternative of OAC
Modified risk scores in AF	Thromboembolic risk: Modified CHA ₂ DS ₂ VASC identified by an algorithm adapted to SNDS data Hemorrhagic risk: Modified HAS-BLED identified by an algorithm adapted to SNDS data

Parameter	Description/Definition
Annual standardized incidence rate of AF	Ratio of number of newly diagnosed non valvular AF patients to the number of individuals in the French population per calendar year (N per 100,000 inhabitants) standardized on age using the 2019 French population structure and 2020 in sensitivity analyses.
Annual prevalence of AF	Ratio of number of diagnosed NVAF patients to the number of individuals in the French population (INSEE data) per calendar year (N per 100,000 inhabitants).

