Data Analysis	
Primary objective
 
In longitudinal analyses, for each AF population (exposed or unexposed to OAC) and subpopulations of interest:
 
The annual incidence rate will be estimated from the occurrence of each of the events of interest, stroke, major bleeding, and death, during patient follow-up. Annual incidence will be defined as the number of events occurring during the follow-up period divided by the number of person-years of follow-up.
 
Secondary objective 2:
 
Patient sociodemographic and clinical characteristics will be analysed through standard descriptive statistics among incident and prevalent AF patients, according to drug exposure (exposed to OAC or unexposed) between 2016 and 2020.
 
Secondary objective 3:
 
In longitudinal analysis, comparison of incidence rate of stroke, major bleeding and death, in AF patients exposed and unexposed to OAC therapy, will be performed using a Cox

regression model adjusted for covariates and with OAC exposure considered as time-dependent variable.

Secondary objective 4:

In cross sectional analyses per calendar year to 2016 to 2020:

- Annual age-standardized incidence rate will be estimated as ratio of number of newly diagnosed non valvular AF patients to the number of individuals at risk in the French population (based on INSEE data) per calendar year (N per 100,000 inhabitants).
- Annual prevalence as ratio of number of diagnosed non valvular AF patients to the number of individuals in the French population (based on INSEE data) per calendar year.

Secondary objective 5:

In longitudinal analysis during the study period, OAC treatment patterns will be described using a treatment sequence analysis, to define lines of treatment (LOT), switches of OAC, concomitant treatments and temporary or permanent discontinuation. A Sunburst for the visualization will be also performed. Persistence rate at 6 and 12 months after initiation of each OAC and any OAC will be estimate with Kaplan-Meier curves.

Secondary objective 6:

In cross-sectional analyses, HCRU (number and rate of patients using each resource by year of follow up) and associated costs (rate per patient per month (PPPM) in Euros) will be compared between AF patients exposed to OAC and unexposed to OAC every year of follow up. Cost analysis will be performed from the health insurance perspective (reimbursed costs).

Milestones	Start of the study: July 2021

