9.2.3 Patient Selection

9.2.3.1 Inclusion Criteria

Patients will be included in the study if they meet the following inclusion criteria:

- Age ≥18 years old at index date

AND

(

- Patients with at least one hospital stay with a principal (PD), related (RD) or associated (AD) diagnosis (in PMSI-MSO) of code I48 (Atrial fibrillation of the International Classification of Disease 10th version, ICD-10) or with an active Long-Term Disease (LTD) with ICD-10 code I48 during the study (historical or inclusion) period

AND/OR

- Patients who are new users of OACs for the AF treatment with or without AF diagnosis (PMSI-MSO or LTD), identifying with a validated and published algorithm with a high specificity (c-index 0,93), using a predictive model developed by Billonnet et al. (16).

)

Description of the algorithm:

The algorithm for identifying patients exposed to OAC indicated for AF will be based on the patients who receive at least one reimbursement of an OAC (VKA, apixaban, rivaroxaban or dabigatran) during the inclusion period, without use of any OAC in the 24 months prior to the first reimbursement date.

Patients reported with at least one orthopedic procedure (osteoarticular or muscular) of the lower limb (including hip/knee replacement) as corresponding to the indication of primary prevention of venous thromboembolic events, during a 6-week period before the first date of OAC delivery will be excluded.

Then, three groups of patients will be identified:

- Confirmed AF are defined as patients with at least one hospital stay with a PD, RD or AD of code I48 or with an active LTD with ICD-10 code I48 or with an electrical cardioversion procedure or radiofrequency ablation before the first date of OAC delivery during the historical period;
- Confirmed DVT/PE are defined as patients hospitalized with a diagnosis of PE (code I26 in any position) or DVT (codes I80 except I80.0, I81, I82 in any position) or with a doppler ultrasound examinations, CT venography, MR venography or pulmonary scintigraphy during a 6-week period before the first date of OAC delivery;
- Unclassified patients in other cases.

Patients with both confirmed AF and DVT/PE will be excluded.

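### SAP 9.7.4.3 divides AF prevalence and incidence by adult residents, but the protocol, the SAP abstract and the output labels describe rates on the whole French population

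*SAP*

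**What the plan says.** Protocol, Appendix 1, Table A1.5 defines annual prevalence as "Ratio of number of diagnosed NVAF patients to the number of individuals in the French population (INSEE data) per calendar year" and annual incidence as "Ratio of number of newly diagnosed non valvular AF patients to the number of individuals in the French population per calendar year". Both are per 100,000 inhabitants, and neither has an age limit.

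The SAP abstract, under secondary objective 4, also gives no age limit. Its incidence denominator is the "number of individuals at risk in the French population (based on INSEE data) per calendar year", and its prevalence denominator is the French population from INSEE data.

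SAP 9.7.4.3 gives two accounts. The narrative says the estimates "will be based on the count of patients living in France as denominator" and "will be expressed per 100,000 inhabitants". The prevalence formula below it divides by the "count of French adult residents from census data in year Y". The incidence formula divides by the count at risk, which "represents French adult residents from census data in year Y minus count of prevalent diagnosed NVAF patients in year Y". The age-group counts used for standardization are defined in the same adult, at-risk way. The footnotes of Tables A12 and A13 state that the estimates are per 100,000 inhabitants.

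The numerator is restricted to adults: SAP 9.2.3.1 requires "Age ≥18 years old at index date".

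**The concern.** One label covers two different quantities. A programmer who follows the formulas produces a rate per 100,000 adults (at risk, for incidence). One who follows the narrative, the abstract or the protocol produces a rate on the whole population. The finished table would not show which was done.

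Objective 4 is a named secondary objective, and Protocol 2.4 foresees the results supporting submissions to French health authorities. A reader who takes an adult-based prevalence labelled per inhabitant and multiplies it by the total population will overstate the number of AF patients. A reader who sets it beside an all-ages rate will see a gap that comes from the denominator alone.

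**Working it through.** The documents state no adult population, adult share or expected rate for this study, so there is no planned figure to reproduce. The check is a ratio of denominators with the numerator held fixed.

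Inputs:
- s, the adult share of the French population. It is not in the documents; assumed range 0.75 to 0.85.
- p, prevalent cases as a share of the total population. About 0.01 is taken from the AF prevalence in the background sections, only to gauge the size of the at-risk subtraction.

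Formulas:
- Prevalence, SAP formula relative to protocol definition: 1/s.
- Incidence, SAP formula relative to protocol definition: 1/(s − p).

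| s | Prevalence ratio | Incidence ratio (p = 0.01) |
|---|---|---|
| 0.75 | 1/0.75 = 1.333 (+33%) | 1/0.74 = 1.351 (+35%) |
| 0.80 | 1/0.80 = 1.250 (+25%) | 1/0.79 = 1.266 (+27%) |
| 0.85 | 1/0.85 = 1.176 (+18%) | 1/0.84 = 1.190 (+19%) |

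A patient count that gives 1,000 per 100,000 inhabitants would thus print as 1,176 to 1,333 under the adult formula. One percentage cannot serve both measures, because the incidence denominator also loses the prevalent cases. The abstract already limits incidence to people at risk. Against that definition the ratio is (1 − p)/(s − p), which is 0.99/0.84 = 1.179 at s = 0.85 and 0.99/0.74 = 1.338 at s = 0.75.

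The documents' own figures allow a rough plausibility check. The study size sections cite 225,747 new OAC users in 2018, and the background cites a standardized rate of 410 per 100,000 for that year. The implied denominator is 225,747/0.00410 = 55.06 million. Protocol Appendix 1 gives over 66 million persons and 98.8% coverage, so the total is about 66.0 million, or 66.0/0.988 = 66.8 million. The ratio of total to implied denominator is 66.0/55.06 = 1.20 to 66.8/55.06 = 1.21, inside the range above. This is only loose support: 410 is a standardized rate, so dividing a crude count by it does not recover a real denominator.

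**The case against.** The best defence is that the formulas are right and only the wording lags. The cohort is aged 18 or over, the denominator is adult, and the adult restriction appears in the prevalence formula, the at-risk count and the age-group counts. The label also follows usage already in the documents: the background describes an annual rate of adult patients and reports it per 100,000 inhabitants. The effect is confined to one descriptive objective and touches no primary event rate, hazard ratio or cost comparison. Since Tables A12 and A13 print N, overall crude figures can be rescaled.

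Most of this stands. The adult denominator is not an arithmetic error and need not change. But a sound denominator under a label that names a different population still misinforms, and rescaling is possible only for a reader who knows which denominator was used. The cited rate shows the same ambiguity and does not resolve it.

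Three stronger readings are tempting, and the documents do not support them:
- A reader might attach a single inflation figure to both measures. That needs an outside adult share, and incidence differs from prevalence in any case.
- A reader might set the SAP prevalence against the background's figure of about 1% of the general population. That figure is for all AF, while the study excludes valvular AF and counts only patients identified from hospital stays, LTD status or the new-user algorithm. The comparison is not like for like on any denominator.
- A reader might take the empty SAP amendment table as proof of an undisclosed departure. That table logs changes to sections of the SAP, not differences from the protocol.

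**Conclusion.** The inconsistency is real, both between the protocol and the SAP and within SAP 9.7.4.3. If the formulas are followed and the labels kept, the published rates are too high as whole-population rates: by about 18% to 33% for prevalence, and 1 to 2 points more for incidence against the protocol definition. These sizes rest on an assumed adult share of 0.85 to 0.75 and, for incidence, on a prevalence of about 1%. The documents supply no adult share, so no single percentage can be stated as fact. This is a fault of definition and labelling in one secondary objective. It merits correction before the tables are produced, and it does not mean that the formulas miscount adults with AF.

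**What to change.** Keep the adult denominator. In SAP 9.7.4.3, the SAP abstract and the footnotes of Tables A12 and A13, label the rates as per 100,000 adult residents (18 and over), adding at risk for incidence. Bring the 9.7.4.3 narrative into line with its formulas, and add a sentence to the SAP stating that this departs from the definitions in Protocol Table A1.5. The cost is wording only; the cohort, the extraction and the computed numbers do not change.

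Optionally, also report the overall crude prevalence and incidence per 100,000 inhabitants using the INSEE total population. It is enough to do this for the overall rows, since both tables are repeated across many subgroups and sensitivity analyses. This addition would not recover the protocol's incidence rate, which is age-standardized to the 2019 French population, so it should be presented as a crude rate only.
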